5.3.1.2. Pharmacokinetic Parameters

Whether actual or nominal PK sampling time will be used for the derivation of PK parameters will be determined by the results of interim PK analyses. If a PK parameter cannot be derived from a patient's concentration data, the parameter will be coded as NC (ie, not calculated). NC values will not be generated beyond the day that a patient discontinues.

In summary tables, statistics will be calculated by setting NC values to missing. Statistics will not be presented for a particular treatment if more than 50% of the data are NC. For statistical analyses (ie, analysis of variance), PK parameters coded as NC will also be set to missing.

If an individual patient has a known biased estimate of a PK parameter (due for example to a deviation from the assigned dose level), this will be footnoted in summary tables and will not be included in the calculation of summary statistics or statistical analyses.

5.3.2. Handling of Incomplete Dates

5.3.2.1. Disease History

Incomplete dates for disease history (eg, initial diagnosis date, date of documented, locally advanced, inoperable or metastatic disease diagnosis, date of response or progression in prior treatment) will be imputed as follows:

- If the day is missing, it will be imputed to the 1st day of the month.
- If both day and month are missing, the month and day will be imputed as January 1st.
- If the date is completely missing, no imputation will be performed.

5.3.2.2. Adverse Events

Incomplete AE-related dates will be imputed as follows:

- If only the day part of the AE onset date is missing, then the AE onset date will be replaced by 1st of the month. For example, if the AE onset date is --/JAN/2015, then the imputed AE onset date will be 01/JAN/2015.
- If both the day and month of the AE onset date are missing, then the onset date will be replaced by January 1st of the year. For example, if AE onset date is --/---/2014, then the imputed AE onset date will be 01/JAN/2014. In all other cases the missing onset day or missing onset month will be replaced by 1

- If after above imputation, the imputed onset date with same month and year of the start of study treatment but less than the start of study treatment, and stop date is not less than the start of study treatment, then the imputed AE onset date will be re-assigned as the start of study treatment.
 - If the AE onset date is missing completely, then the onset date will be imputed as following: If not missing the visit date and visit date is less than the start of study treatment and less than or equal to the stop date, then the visit date will be used to impute the onset date.
 - Else if previous visit date is greater than or equal to the start of study treatment and less than or equal to the stop date, then the previous visit date will be used to impute the onset date.
 - Else if previous visit date is less than the start of study treatment and the start of study treatment is less than or equal to stop date, then the start of study treatment will be used to impute the onset date.
 - Else Stop date will be used to impute the onset date.
- Incomplete stop date will be replaced by the last day of the month (if day is missing only).
- Incomplete stop date will be replaced by the last month of the year (if month is missing).
- If the AE stop date is missing completely and still present, then the stop date will be imputed as following:
 - If not missing death date, then death date will be used to impute the stop date.
 - Else if not missing withdraw date or Date Decision to Discontinue Treatment, the stop date will be imputed as the maximum of Withdrawal date, Date Decision to Discontinue Treatment, Onset date or AE visit date.
 - Else if missing withdraw date and Date Decision to Discontinue Treatment, the stop date will be imputed as the maximum of subject summary visit date, Onset date or AE visit date.
 - Else the stop date will be imputed as the maximum of onset date or last dosing date.
- If the AE stop date is missing completely and event resolved, then the stop date will be imputed as following:
 - If visit date is greater than onset date, then the visit date will be used to impute the stop date.
 - Else the onset date will be used to impute the stop date.

- If after above imputation, the imputed stop date is less than the start of study treatment, then the imputed AE stop date will be re-assigned as the start of study treatment.
- In all other cases the incomplete stop date will not be imputed. If stop date of AE is after date of cut-off outcome of AE is ongoing at cut-off.

5.3.2.3. Prior and Concomitant Medications

Incomplete prior/concomitant medication dates will be imputed as follows:

- If the medication date is missing completely, no imputation will be performed.
- If the day of medication date is missing, then the medication date will be replaced by 1st of the month. For example, if the medication start date is --/JAN/2015, then the imputed medication start date will be 01/JAN/2015.
- If both the day and month of medication start date are missing, then the medication date will be replaced by January 1st of the year. For example, if the medication start date is --/--/2014, then the imputed medication start date will be 01/JAN/2014.
- In all other cases the missing medication day or missing medication month will be replaced by 1.
- Incomplete stop date will be replaced by the last day of the month (if day is missing).
- Incomplete stop date will be replaced by the last month of the year (if month is missing).
- In all other cases the incomplete medication stop date will not be imputed.

5.3.2.4. Exposure

No imputation will be done for first dose date or last dose date.

5.3.3. Imputation Rules for Date of Last Contact and Efficacy Assessments

5.3.3.1. Date of Last Contact

The date of last contact will be derived for patients not known to have died at the analysis cut-off using the latest complete date among the following:

- All patient assessment dates (blood draws (laboratory, PK), vital signs, performance status, ECG, tumor assessments).
- Start and end dates of anti-cancer therapies administered after study treatment discontinuation.
- AE start and end dates.
- Last date of contact collected on the 'Survival Follow-up' eCRF (do not use date of survival follow-up assessment unless status is 'alive').

- Study drug start and end dates.
- Randomization date for the randomized cohorts and enrollment date for the non-randomized cohorts.
- Date of discontinuation on disposition eCRF pages (do not use if reason for discontinuation is lost to follow-up).

Only dates associated with actual examinations of the patient will be used in the derivation. Dates associated with a technical operation unrelated to patient status such as the date a blood sample was processed will not be used. Assessment dates after the cut-off date will not be applied to derive the last contact date.

5.3.3.2. Death Date

Partial death dates will be imputed based on the last contact date:

- If the day or both the day and the month is missing, death will be imputed to the maximum of the full (non-imputed) day after the date of last contact and the following:
 - Missing day: 1st day of the month and year of death.
 - Missing day and month: January 1st of the year of death.

5.3.3.3. Tumor Assessments

All investigation dates (eg, X-ray, CT scan) must be completed with day, month and year.

If there are multiple scan dates associated with an evaluation, ie, radiological assessments occur over a series of days rather than the same day, the choice of date of assessment could impact the date of progression and/or date of response. If there are multiple scan dates associated with an evaluation, the earliest of the scan dates associated with the evaluation will be used as the date of assessment.

If one or more investigation dates for an evaluation are incomplete but other investigation dates are available, the incomplete date(s) are not considered for calculation of the assessment date and assessment date is calculated as the earliest of all investigation dates (eg, X-ray, CT-scan).

If all measurement dates for an evaluation have no day recorded, the 1st of the month is used.

If the month is not completed, for any of the investigations for an evaluation, the respective assessment will be considered to be at the date which is exactly between the previous and the following assessment. If both a previous and following assessments are not available, this assessment will not be used for any calculations.

5.3.3.4. Date of Start of New Anti-cancer Therapy

Incomplete dates for start date of new anti-cancer therapy (drug therapy, radiation) will be imputed as follows and will be used for determining censoring dates for efficacy analyses and in the derivation of the end of on-treatment period.

- If the end date of new anti-cancer therapy is:
 - completely missing then it will be ignored in the imputations below.
 - partially missing with only year (YYYY) available then the imputations below will consider 31DECYYYY as the end date of the new anti-cancer therapy.
 - partially missing with only month and year available then the imputations below will consider the last day of the month for MMMYYYY as the end date of the new anti-cancer therapy.
- If the start date of new anti-cancer therapy is completely or partially missing then the imputed start date of new anti-cancer therapy is:
 - completely missing then it will be ignored in the imputations below.
 - partially missing with only year (YYYY) available then the imputations below will consider 01JANYYYY as the start date of the new anti-cancer therapy.
 - partially missing with only month and year available then the imputations below will consider the first day of the month for MMMYYYY as the start date of the new anti-cancer therapy.

6. ANALYSES AND SUMMARIES

Refer to [Section 4](#) for definitions of analysis sets and [Section 5.2](#) for general methodology.

6.1. Primary Endpoints

6.1.1. DLT (Dose-escalation Cohorts)

6.1.1.1. Primary Analysis

The primary analyses will be based on the DLT-evaluable set. DLTs will be listed and summarized by treatment group.

6.1.2. Objective Response as Assessed by the Investigator (Expansion Cohorts)

6.1.2.1. Primary Analysis

Refer to [Section 6.2.2.1](#).

6.2. Secondary Endpoint(s)

6.2.1. Safety Endpoints

Refer to [Section 6.6](#).

6.2.2. Efficacy Endpoints

The following analyses will be based on the FAS by treatment group. Assessment of response will be made using RECIST v1.1 for solid tumors and Cheson 2007 criteria for NHL.

6.2.2.1. Objective Response as Assessed by the Investigator

BOR will be assessed based on reported overall lesion responses at different evaluation time points from the 'start date' until documented disease progression, according to the following rules. Only tumor assessments performed before the start of any further anti-cancer therapies will be considered in the assessment of BOR. Clinical deterioration will not be considered as documented disease progression.

BOR Based on Confirmed Responses for Solid Tumors

- CR = at least two determinations of CR at least 4 weeks apart and before progression.
- PR = at least two determinations of PR or better (PR followed by PR or PR followed by CR) at least 4 weeks apart and before progression (and not qualifying for a CR).
- SD (applicable only to patients with measurable disease at baseline) = at least one SD assessment (or better) \geq 6 weeks after 'start date' and before progression (and not qualifying for CR or PR).
- Non-CR/non-PD (applicable only to patients with non-measurable disease at baseline) = at least one non-CR/non-PD assessment (or better) \geq 6 weeks after 'start date' and before progression (and not qualifying for CR or PR).
- PD = progression \leq 12 weeks after 'start date' (and not qualifying for CR, PR, SD or non-CR/non-PD).
- Not Evaluable (NE): all other cases.

An objective status of PR or SD cannot follow one of CR. SD can follow PR only in the rare case that tumor increases by less than 20% from the nadir, but enough that a previously documented 30% decrease from baseline no longer holds. If this occurs, the sequence PR-SD-PR is considered a confirmed PR. A sequence of PR – SD – SD – PD would be a best response of SD if the window for SD definition has been met.

Objective Response (OR) is defined as confirmed BOR of CR or PR according to RECIST v1.1.

Patients who do not have an on-treatment radiographic tumor assessment due to early progression, who receive anti-tumor therapies other than the study treatments prior to reaching a CR or PR, or who die, progress, or drop out for any reason prior to reaching a CR or PR will be counted as non-responders in the assessment of OR. Each patient will have an objective response status (0: no OR; 1: OR). OR rate (ORR) is the proportion of patients with OR in the analysis set.

ORR by treatment group will be calculated along with the 2-sided 95% CI using the Clopper-Pearson method (exact CI for a binomial proportion as computed by default by the FREQ procedure using the EXACT option).

In addition, the frequency (number and percentage) of patients with confirmed BOR of CR, PR, SD, PD, non-CR/non-PD (applicable only to patients with non-measurable disease at baseline), and NE will be tabulated. Patients with BOR of NE will be summarized by reason for having NE status. The following reasons will be used:

- No baseline assessment.
- No post-baseline assessments due to death.
- No post-baseline assessments due to other reasons.
- All post-baseline assessments have overall response NE.
- New anti-cancer therapy started before first post-baseline assessment.
- SD or non-CR/non-PD of insufficient duration (<6 weeks after 'start date').
- PD too late (>12 weeks after 'start date').

Special and rare cases where BOR is NE due to both early SD or non-CR/non-PD and late PD will be classified as 'SD too early'.

BOR Based on Unconfirmed Responses for NHL:

- CR = one objective status of CR documented before progression.
- PR = one objective status of PR documented before progression (and not qualifying for CR).
- SD = at least one SD assessment (or better) ≥ 6 weeks after 'start date' and before progression (and not qualifying for CR or PR).
- PD = progression ≤ 12 weeks after 'start date' (and not qualifying for CR, PR, or SD).
- NE: all other cases.

An objective status of PR or SD cannot follow one of CR. SD can follow PR only in the rare case that tumor increases by less than 50% from the nadir, but enough that a previously documented 50% decrease from baseline no longer holds (see [Section 6.2.2.2](#) on details of tumor change).

OR is defined as BOR of CR or PR according to Cheson 2007 criteria.

Patients who do not have an on-treatment radiographic tumor assessment due to early progression, who receive anti-tumor therapies other than the study treatments prior to reaching a CR or PR, or who die, progress, or drop out for any reason prior to reaching a CR or PR will be counted as non-responders in the assessment of OR. Each patient will have an objective response status (0: no OR; 1: OR). OR rate (ORR) is the proportion of patients with OR in the analysis set.

ORR by treatment group will be calculated along with the 2-sided 95% CI using the Clopper-Pearson method (exact CI for a binomial proportion as computed by default by the FREQ procedure using the EXACT option).

In addition, the frequency (number and percentage) of patients with a BOR of CR, PR, SD, PD, and NE will be tabulated. Patients with BOR of NE will be summarized by reason for having NE status. The following reasons will be used:

- No baseline assessments.
- No post-baseline assessments due to death.
- No post-baseline assessments due to other reasons.
- All post-baseline assessments have overall response NE.
- New anti-cancer therapy started before first post-baseline assessment.
- SD of insufficient duration (<6 weeks after 'start date').
- PD too late (>12 weeks after 'start date').

Special and rare cases where BOR is NE due to both early SD and late PD will be classified as 'SD too early'.

6.2.2.2. Tumor Shrinkage

Tumor Shrinkage for Solid Tumors:

Tumor shrinkage will be summarized as the percent change from baseline in target lesions (sum of longest diameter for non-nodal lesion and short axis for nodal lesion) per time point. It will be derived as:

- $((\text{Sum of target lesions at week XX} - \text{sum of target lesions at baseline}) / \text{sum of target lesions at baseline}) \times 100$.

The maximum reduction in target lesions from baseline will be derived across all the post-baseline assessments until documented disease progression, excluding assessments after start of subsequent anticancer therapy, as:

- Minimum of $((\text{sum of target lesions at week XX} - \text{sum of target lesions at baseline}) / \text{sum of target lesions at baseline}) \times 100$.

A waterfall plot of maximum percent reduction in the sum of longest diameter for non-nodal lesions and short axis for nodal lesions from baseline will be created. This plot will display the best percentage change from baseline in the sum of the diameter of all target lesions for each patient with measurable disease at baseline and at least one adequate post-baseline assessment.

Tumor Shrinkage for NHL:

The greatest transverse diameter and the greatest perpendicular transverse diameter will be recorded for each index lesion. The product of these 2 dimensions will be recorded and the sum of the product diameters (SPD) of the index lesions will be the baseline value used in determining response and tumor shrinkage.

Tumor shrinkage will be summarized as the percent change from baseline in index lesions (SPD) per time point. It will be derived as:

- $((\text{SPD at week XX} - \text{SPD at baseline}) / \text{SPD at baseline}) \times 100$.

The maximum reduction in index lesions from baseline will be derived across all the post-baseline assessments until documented disease progression, excluding assessments after start of subsequent anticancer therapy, as:

- Minimum of $((\text{SPD at week XX} - \text{SPD at baseline}) / \text{SPD at baseline}) \times 100$.

A waterfall plot of maximum percent reduction in the SPD from baseline will be created. This plot will display the best percentage change from baseline in the SPD for each patient with measurable disease at baseline and at least one adequate post-baseline assessment.

6.2.2.3. Duration of Response

Duration of Response (DR) is defined, for patients with OR, as the time from first documentation of objective response (CR or PR) to the date of first documentation of objective progression of disease (PD) or death due to any cause. If a patient has not had an event (PD or death), DR is censored at the date of last adequate tumor assessment. The censoring rules for DR are as described below for PFS in [Table 3](#).

$$\text{DR (months)} = [\text{date of event or censoring} - \text{first date of OR} + 1] / 30.4375$$

Kaplan-Meier estimates (product-limit estimates) will be presented by treatment group together with a summary of associated statistics including the median DR time with 2-sided 95% CIs. In particular, the DR rate at 3, 6 and 12 months will be estimated with corresponding 2-sided 95% CIs. The CIs for the median will be calculated according to Brookmeyer and Crowley and the CIs for the survival function estimates at the time points defined above will be derived using the log-log transformation according to Kalbfleisch and Prentice (conftype=loglog default option in SAS Proc LIFETEST) with back transformation to a CI on the untransformed scale. The estimate of the standard error will be computed using Greenwood's formula.

DR will be displayed graphically and analyzed using Kaplan-Meier methodology. If the number of patients with OR is small, the Kaplan-Meier method may not provide reliable estimates. In this case, only descriptive statistics or listings will be provided.

6.2.2.4. Time to Response

Time to response (TTR) is defined, for patients with OR, as the time from the ‘start date’ to the first documentation of objective response (CR or PR). For RECIST-defined response in solid tumors confirmation of response is required.

$$\text{TTR (in months)} = [\text{first date of OR} - \text{‘start date’} + 1] / 30.4375$$

TTR will be summarized using simple descriptive statistics (mean, SD, median, min, max, Q1, Q3).

6.2.2.5. Progression-free Survival

Progression-Free Survival (PFS) is defined as the time from ‘start date’ to the date of the first documentation of objective progression of disease (PD) or death due to any cause, whichever occurs first.

PFS data will be censored on the date of the last adequate tumor assessment for patients who do not have an event (PD or death), or for patients with an event after 2 or more missing tumor assessments. For patients who start a new anti-cancer therapy prior to an event, PFS data will be censored on the date of the last adequate tumor assessment prior to starting the new anti-cancer therapy. Patients who do not have an adequate baseline tumor assessment or who do not have an adequate post-baseline tumor assessment will be censored on the ‘start date’ unless death occurred on or before the time of the second planned tumor assessment (ie, ≤ 16 weeks after ‘start date’) in which case the death will be considered an event ([Table 3](#)).

In this study antitumor activity will be assessed through radiological tumor assessments conducted at screening and every 8 weeks until disease progression regardless of initiation of subsequent anti-cancer therapy. After 10 months from ‘start date’, tumor assessments will be conducted less frequently, ie, at 16-week intervals.

The censoring and event date options to be considered for the PFS and DR analysis are presented in [Table 3](#).

$$\text{PFS (months)} = [\text{date of event or censoring} - \text{‘start date’} + 1] / 30.4375$$

Table 3. Outcome and Event Dates for PFS and DR Analyses

Scenario	Date of event/censoring	Outcome
No adequate baseline assessment	'Start date' ^a	Censored ^a
PD or death - After at most one missing or inadequate post-baseline tumor assessment, OR - ≤ 16 weeks after 'start date'	Date of PD or death	Event
PD or death after 2 or more missing or inadequate post-baseline tumor assessments	Date of last adequate tumor assessment ^b documenting no PD before new anti-cancer therapy is given or missed tumor assessments	Censored
No PD and no death	Date of last adequate tumor assessment ^b documenting no PD before new anti-cancer therapy is given or missed tumor assessments	Censored
Treatment discontinuation due to 'Disease progression' without documented progression	Not applicable	Information is ignored. Outcome is derived based on documented progression only.
New anti-cancer therapy given	Date of last adequate tumor assessment ^b documenting no PD before new anti-cancer therapy is given or missed tumor assessments	Censored

^a However if the patient dies ≤16 weeks after 'start date' the death is an event with date on death date.

^b If there are no adequate post-baseline assessments prior to the PD or death, then the time without adequate assessment should be measured from the 'start date'; if the criteria were met the censoring will be on the 'start date'

Kaplan-Meier estimates (product-limit estimates) will be presented by treatment group together with a summary of associated statistics including the median PFS time with 2-sided 95% CIs. In particular, the PFS rate at 3, 6, 9, 12 and 15 months will be estimated with corresponding 2-sided 95% CIs. The CIs for the median will be calculated according to Brookmeyer and Crowley and the CIs for the survival function estimates at the time points defined above will be derived using the log-log transformation according to Kalbfleisch and Prentice (conftype=loglog default option in SAS Proc LIFETEST) with back transformation to a CI on the untransformed scale. The estimate of the standard error will be computed using Greenwood's formula.

Frequency (number and percentage) of patients with each event type (PD or death) and censoring reasons will be presented by treatment group. Reasons for censoring will be summarized according to the categories in [Table 4](#) following the hierarchy shown.

Table 4. PFS Censoring Reasons and Hierarchy

Hierarchy	Condition	Censoring Reason
1	No adequate baseline assessment	No adequate baseline assessment
2	Start of new anti-cancer therapy before event.	Start of new anti-cancer therapy
3	Event after 2 or more missing or inadequate post-baseline tumor assessments/'start date'	Event after missing assessments ^a
4	No event and [withdrawal of consent date ≥ 'start date' OR End of study (EOS) = Subject refused further follow-up]	Withdrawal of consent
5	No event and lost to follow-up in any disposition page	Lost to follow-up
6	No event and [EOS present OR disposition page for any epoch after screening says patient will not continue into any subsequent phase of the study] and no adequate post-baseline tumor assessment	No adequate post-baseline tumor assessment
7	No event and none of the conditions in the prior hierarchy are met	Ongoing without an event

^a 2 or more missing or inadequate post-baseline tumor assessments.

The PFS time or censoring time and the reasons for censoring will also be presented in a patient listing.

Time of Follow-Up for PFS

A plot will be generated to compare planned and actual relative day of tumor assessments by treatment group. A Kaplan-Meier plot for PFS follow-up duration will also be generated to assess the follow-up time in the treatment groups reversing the PFS censoring and event indicators.

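### SAP 6.2.2.5 states the wrong scan interval for patients off treatment, so for early stoppers one missed follow-up scan can count as two or three and censor a PFS or DR event

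*SAP*

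**What the plan says.** SAP 6.2.2.5 describes radiological assessments as "conducted at screening and every 8 weeks until disease progression regardless of initiation of subsequent anti-cancer therapy". After 10 months from the start date, "tumor assessments will be conducted less frequently, ie, at 16-week intervals". The legible SAP text gives no other schedule.

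SAP Table 3 uses this for censoring. Progression (PD) or death is an event if it comes "After at most one missing or inadequate post-baseline tumor assessment", or within 16 weeks of the start date. "PD or death after 2 or more missing or inadequate post-baseline tumor assessments" is censored at the last adequate assessment. SAP Table 4, row 3, repeats the threshold as a censoring reason: "Event after 2 or more missing or inadequate post-baseline tumor assessments". SAP 6.2.2.3 extends the rule to DR: "The censoring rules for DR are as described below for PFS in" Table 3.

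The protocol differs. Table 5 footnote 22 (and Table 1 footnote 19 for dose escalation) limits 8-weekly scanning to the first 10 months on study treatment, with a ±1 week window and 16-weekly scans after that. Protocol 3.1.3 and 6.3 put every patient whose treatment ends without PD on 16-weekly assessments, whenever that happens. A scan is repeated at the End of Treatment (EOT) visit, about 28 days after the last dose, only if more than 6 weeks have passed since the previous one. The protocol does not say whether the 16 weeks run from the last scan or from EOT.

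**The concern.** Table 3 is meant to tolerate one missed assessment. To count misses one needs a list of planned visits, and the only list in the SAP has twice as many visits as the protocol for a patient who stops treatment without PD in the first 10 months. Visits that no site was asked to make could then count as missing.

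This is more than silence about off-treatment patients. Protocol 5.7.1 bars other anticancer therapy during study therapy, so a schedule that continues regardless of subsequent therapy does describe the off-treatment period, with the wrong interval. The SAP may modify planned analyses (SAP 2), but it cannot change when sites scanned.

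At stake are true PFS and DR events recorded as censored at an earlier scan. Table 4 and the patient listing would show them as events after missing assessments, without showing that only one protocol scan was missed. The SAP also promises this display: "A plot will be generated to compare planned and actual relative day of tumor assessments by treatment group". In it, patients correctly following the off-treatment schedule would look off-schedule.

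**Working it through.** **Inputs.** 8-week and 16-week intervals and the 10-month switch (SAP 6.2.2.5); 1 month = 30.4375 days (SAP 5.2.8); censoring at 2 or more missing (SAP Table 3); 16-weekly follow-up and ±1 week window (protocol Table 5 footnote 22).

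**The SAP's own figure.** It allows for a death "on or before the time of the second planned tumor assessment", glossed as 16 weeks from the start date: 2 × 8 = 16, reproduced.

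**SAP visit list.** 10 months = 10 × 30.4375 / 7 = 43.5 weeks. Visits fall at weeks 8, 16, 24, 32, 40, then 56, 72, 88. The SAP does not fix the first 16-weekly visit, so 40-then-56 is an assumption. The alternative is 40, 48, then 64, 80.

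**Counting rule (assumed).** A visit is missing if its +1 week window closes before the event and no scan falls within ±1 week of it.

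**One missed follow-up scan, PD at the next, timed from the last scan.** With the last scan at week w, the scan at w + 16 is missed and PD is found at w + 32.

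| Last scan | PD at | SAP visits missing (40-then-56) | Count | Count if week 48 is the last 8-weekly visit | Count on protocol schedule |
|---|---|---|---|---|---|
| 8 | 40 | 16, 24, 32 | 3 | 3 | 1 |
| 16 | 48 | 24, 32, 40 | 3 | 3 | 1 |
| 24 | 56 | 32, 40 | 2 | 3 | 1 |
| 32 | 64 | 40, 56 | 2 | 2 | 1 |
| 40 | 72 | 56 | 1 | 2 | 1 |
| 56 | 88 | 72 | 1 | not a visit | 1 |

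A count of 2 or more moves the patient from an event at w + 32 to censoring at w, which is 32 × 7 / 30.4375 = 7.4 months earlier.

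**Deaths** between the close of the missed scan's window (w + 17) and the next due scan (w + 32), on the 40-then-56 list: always censored for last scan week 8, 16 or 24. For week 32, a second SAP visit is missed only after week 57, so the share of that interval leading to censoring is (64 − 57) / (64 − 49) = 47%. For week 40, never.

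**Fully compliant patients.** Timed from an on-schedule last scan, none reaches 2. Other patterns do:
- Scan week 16, EOT week 20 (no scan due), follow-up timed from EOT, PD week 36: visits 24 and 32 missing, count 2.
- Scan week 8, EOT scan week 14.5 (6.5 weeks later, so due), PD week 30.5: visits 16 and 24 missing, count 2.
- Response week 8, confirmation scan week 12, treatment stops, PD week 28: visits 16 and 24 missing, count 2.

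**Limit of the week-56 statement.** It applies when follow-up is timed from an on-schedule last scan. With EOT 4 weeks after a week-56 scan and follow-up timed from EOT, scans are due at weeks 76 and 92. Missing the first leaves visits 72 and 88 uncovered, so the count is again 2.

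**Illustrative size, on assumed inputs.** A simulation compared SAP-schedule counting with counting in 16-week off-treatment steps. It assumed that 5–20% stop without PD before 10 months, that each follow-up scan has a 0–30% chance of being missed, that 20% of events are deaths, and that median PFS is 4 months (20 melanoma patients) or 11 months (80 follicular lymphoma patients). Stopping was unrelated to prognosis, and no new therapy preceded the event, which makes this an upper range.

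| Follow-up timed from | Events censored after 0 or 1 missed scans, per 20 | Per 80 | Largest shift in PFS rate at 6 or 12 months |
|---|---|---|---|
| Last scan | 0–0.8 | 0–2.5 | 0.7 points |
| EOT | 0.2–1.3 | 0.3–4.0 | 1.3 points |

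For scale, SAP 5.1.1 gives maximum standard errors of a response rate of 11 points (n = 20) and 6 points (n = 80).

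**The case against.** The strongest reply is that the SAP never says misses are counted on the 6.2.2.5 schedule. A scan the protocol did not schedule is not naturally missing, and a programmer using the protocol schedule loses none of these events. The 16-week gloss fits the protocol's on-treatment schedule equally well, and the planned-versus-actual plot does not define planned. Footnote b to Table 3 speaks of time without adequate assessment, which may hint at an elapsed-time rule.

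This stands to the extent that the consequence is conditional. It does not remove the misstatement: the schedule in the SAP is wrong for these patients, and it is the only one a programmer working from the SAP has. An elapsed-time rule would also need an interval between planned scans, and the SAP's intervals are the ones in 6.2.2.5.

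A reader might infer that one missed scan usually costs the event for anyone followed off treatment. The documents do not support that. Treatment may run for 2 years, and no distribution of stopping times is given. On an assumed exponential time to stopping with median 8, 16, 26 or 52 weeks, 94%, 75%, 57% or 35% of last-scan positions give a count of 2 or more (40-then-56 list, follow-up timed from the last scan). A reader might also infer that compliant patients are safe unless follow-up runs from an EOT visit without a scan; the week-14.5 and week-12 examples show otherwise.

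Materiality is low, as the objection says. No hypothesis is tested (SAP 5.1.1), new therapy before the event censors the patient anyway, and censoring reasons are tabulated and listed.

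**Conclusion.** The point holds as a minor error in the SAP's stated schedule. SAP 6.2.2.5 contradicts the protocol for patients whose treatment ends without PD in about the first 10 months. If Table 3 misses are counted on that schedule, one missed follow-up scan censors the next PD for last scans at about weeks 8 to 32. Week 40 depends on the undefined switch visit.

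The conclusion rests on the assumed counting rule and ±1 week window, on no new therapy starting first, and on legible text only, since parts of the SAP are redacted. The number of patients is unknown. The documents do not support reading this as a threat to the trial's main conclusions: objective response and overall survival do not use Table 3, and PFS and DR are descriptive secondary endpoints.

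**What to change.** In SAP 6.2.2.5, replace the schedule with the protocol's: 8-weekly on treatment to 10 months, then 16-weekly from 10 months or from end of treatment without PD, whichever comes first. It would help to name the last 8-weekly visit (week 40 or 48).

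In Table 3 (PFS and DR) and Table 4 row 3, state that an assessment is missing only if it was due under the protocol schedule applying to that patient at that time. Count off-treatment scans in 16-week steps and allow the protocol's visit window. State whether the steps run from the last scan or from EOT.

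A sensitivity analysis counting every PD and death as an event, regardless of missed scans, is optional.

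The cost is a few sentences and one derivation. Dosing, EOT and scan dates are already collected, and no extra scans or data are needed.
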